5.2. ASSESSMENT OF AES

All AEs, regardless of severity, occurring following study drug administration by a subject must be recorded on the AE worksheet. This will include the following information:

- Description of the AE
- Date of onset
- Duration
- Frequency
- Severity
- Seriousness (yes/no)
- Treatment
- Outcome
- Relationship to study medication, injection procedure and/or underlying disease

All AEs and SAEs must be followed until resolution, or the condition stabilizes. The Investigator is responsible to ensure that follow-up includes any supplemental investigations as may be indicated to elucidate as completely as possible the nature and/or causality of the AE or SAE. This may include additional laboratory tests or investigations, histopathological examinations, or consultation with other health care professionals. The Sponsor or its designee may request that the Investigator perform or arrange for the conduct of supplemental measurements and/or evaluations.

5.2.1. **AE CAUSALITY**

The study investigator will determine whether an AE is related or unrelated to study medication, the procedure (intramuscular injection) and / or the underlying disease using the following criteria:

Not related: An adverse event that is not related to the use of the test article or administration procedure.

Possibly related: An adverse event that might be due to the use of the test article or administration procedure. An alternative explanation, e.g., concomitant study

product(s), concomitant disease(s), is inconclusive. The relationship in time is reasonable; therefore, a causal relationship cannot be excluded.

Probably related: An adverse event that might be due to the use of the test article or administration procedure. The relationship in time is suggestive. An alternative explanation is less likely, e.g., concomitant drug(s), concomitant disease(s).

Definitely related: An AE that is due to the use of the test article or administration procedure. The event cannot be reasonably explained by an alternative explanation – e.g., concomitant drug(s), concomitant disease(s).

5.2.2. AE INTENSITY

The intensity of the AE/SAE will be defined by the following criteria:

Mild: The AE is noticeable to the subject but does not interfere with

routine activity.

Moderate: The AE is discomforting and interferes with routine activity. Severe: The AE significantly limits the subject's ability to perform

routine activities despite symptomatic therapy.

5.3. REPORTING/RECORDING OF AES

Throughout the course of the study, all efforts will be made by the investigator to remain alert to possible AEs. The first concern will be the safety of the subject, and for providing appropriate medical intervention. The period of observation for collection of AEs starts during the first intramuscular injection procedure (Day 0) until the Day 365 follow-up safety extension visit. Any AE should be recorded on the appropriate study worksheet.

5.4. REPORTING / RECORDING OF SAES

5.4.1. INVESTIGATOR'S RESPONSIBILITY

SAEs will be recorded following the first study drug administration through the Day 365 safety extension follow-up visit. Any serious adverse event or unexpected adverse event that occurs during this investigation, whether or not related to the study medication, must be reported as soon as possible but no later than 3 working days after the investigator first learns of the event to the Sponsor and the designated CRO by completing the SAE form and the AE information in the EDC and selecting appropriate criteria that classifies the AE as serious and/or unexpected. In order to have the Investigator's signature on file, the signed SAE form needs to be uploaded to the EDC at the time of initial data entry.

Each SAE must be followed with appropriate medical management until resolved or assessed as chronic or stable regardless of whether or not, in the opinion of the Investigator, the event is thought to be related to the study medication.

The Investigator will be required to provide complete information (including the Investigator's opinion of the relationship of the SAE to the study medication) concerning each SAE to the CRO and Sponsor within 5 working days of first learning of the event. This information must be recorded in the subject's medical record and then entered into the EDC. Copies of related source documentation such as results/reports, hospitalization records, and other relevant information must be obtained if possible.

In the event of an SAE leading to hospitalization, every effort will be made by the investigational site to obtain medical records, including a hospital discharge summary. In the event of a fatal AE, documentation of any available postmortem findings, including autopsy, will be provided to the Sponsor or their designee. In any event, the Investigator will provide a narrative summary of circumstances, events related to the death, and cause of death, if known.

The Investigator must comply with the applicable local regulatory requirements related to the reporting of SAEs to regulatory authorities and the Institutional Review Board (IRB), and Institutional Biosafety Committee (IBC) if applicable. Upon receipt from the Sponsor of an initial or follow-up IND Safety Report or other safety information, the Investigator must promptly notify his or her IRB, and IBC (if applicable).

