2. GOOD CLINICAL PRACTICES (GCP) STATEMENT

This trial will be conducted in compliance with all applicable federal regulations pertaining to investigational drugs and devices including but not limited to: 21 CFR Part 50, Part 54, Part 56, Part 312, and GCP standards. This trial will be conducted in compliance with the protocol as approved by an Institutional Review Board (IRB). Any deviations from the protocol that may affect the safety and welfare of study participants will be immediately reported to the Sponsor and to the IRB per each institution's guidelines.

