5.4.2. SPONSOR'S RESPONSIBILITY

All AEs and SAEs will be reported on an annual basis to FDA in accordance with the IND regulation (21 CFR Part 312). Per the 2010 FDA Guidance Document for Industry and Investigators "Safety Reporting Requirements for INDs and BA/BE Studies," events categorized as 'possibly' or 'probably' related will be treated as 'suspected adverse reactions.' Events categorized as 'definitely' related will be treated as an 'adverse reaction.'

All serious, unexpected adverse reactions and suspected adverse reactions will be reported to FDA and to all participating investigators as an IND Safety Report within 15 calendar days of the event after the sponsor determines that the suspected adverse reaction qualifies for reporting (21 CFR §312.32). Any unexpected fatal or life-threatening AEs will be reported to the Agency within 7 calendar days after the sponsor's initial receipt of the information.

The Sponsor will notify all participating investigators of any new safety information that alters the current risk-benefit assessment of the study medication or that would be sufficient to consider changes in VM202 administration or in the overall conduct of the trial.

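### Sites may take 3 working days to give first notice of any SAE, deaths included, so an unexpected fatal event can reach FDA as late as day 12 with every limit met

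*Protocol*

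**What the plan says.** Protocol section 5.4.1 (Investigator's Responsibility) sets two clocks, both starting when the investigator learns of the event.

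- **First notice.** The event "must be reported as soon as possible but no later than 3 working days after the investigator first learns of the event". The route is "by completing the SAE form and the AE information in the EDC", and the site also selects there the criteria that classify the event as serious and/or unexpected. So that a signature is on file, "the signed SAE form needs to be uploaded to the EDC at the time of initial data entry". No shorter limit is given for a death or a life-threatening event.
- **Complete information.** This includes the investigator's opinion on relationship to study medication. It is owed "concerning each SAE to the CRO and Sponsor within 5 working days of first learning of the event".

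Protocol section 5.4.2 (Sponsor's Responsibility) sets a third clock, in calendar days and from a different start: "Any unexpected fatal or life-threatening AEs will be reported to the Agency within 7 calendar days after the sponsor's initial receipt of the information". The 15-day IND Safety Report in the same section runs from the sponsor's determination that an event qualifies. Section 5.4.2 uses the relationship categories to decide what counts as a suspected adverse reaction.

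Protocol section 2 applies a different standard to another kind of event: "Any deviations from the protocol that may affect the safety and welfare of study participants will be immediately reported to the Sponsor", and also to the IRB.

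**The concern.** A death may be notified days later than a protocol deviation that merely might affect safety. The site clocks count working days and the sponsor clock counts calendar days from receipt, so the protocol never shows the total time from the site to FDA. The requirement to upload a signed form at initial entry can also hold back the alert when the investigator is away.

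The causality opinion is due on a clock that takes no account of when the sponsor must file. A site that notifies promptly starts the sponsor's 7 days early but keeps its own 5 working days for the opinion.

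Adverse events are the primary endpoint (Protocol section 5.6.1), all reported adverse events go to the DSMB (section 5.6.4), and the sponsor must tell investigators of new safety information (section 5.4.2). Late first notice delays the last two. It does not change whether an event is counted.

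**Working it through.** The documents state no total time from site to FDA, so there is no figure to reproduce. The check is a calendar count.

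**Inputs**
- First notice: 3 working days from the investigator's awareness (section 5.4.1).
- Complete information with causality: 5 working days from the same start (section 5.4.1).
- Report to FDA of an unexpected fatal or life-threatening event: 7 calendar days from sponsor receipt (section 5.4.2).
- Assumption: the protocol does not define a working day. I take Monday to Friday, with the day of awareness as day 0. The holiday columns put one weekday holiday in the seven days after awareness.

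**Step 1. Working days as calendar days**

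| Aware on | 3 working days | with a holiday | 5 working days | with a holiday |
|---|---|---|---|---|
| Mon | 3 | 3 or 4 | 7 | 8 |
| Tue | 3 | 3 or 6 | 7 | 8 |
| Wed | 5 | 5 or 6 | 7 | 8 |
| Thu | 5 | 5 or 6 | 7 | 8 |
| Fri | 5 | 5 or 6 | 7 | 10 |
| Sat | 4 | 4 or 5 | 6 | 9 |
| Sun | 3 | 3 or 4 | 5 | 8 |

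**Step 2. Awareness to FDA.** Let R be the calendar day on which the sponsor receives first notice. The FDA report is due on day R + 7.
- Longest R without a holiday: 5 + 7 = 12.
- Longest R with a holiday: 6 + 7 = 13.
- Notice within one day: 1 + 7 = 8, which is 4 days sooner than 12 and 5 sooner than 13.

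**Step 3. Causality against the FDA report.** Let C be the day on which causality falls due (the 5-working-day columns). The margin is (R + 7) − C.
- Same-day notice, weekday, no holiday: 0 + 7 − 7 = 0 days. For Saturday it is 7 − 6 = 1, and for Sunday 7 − 5 = 2.
- Same-day notice with a holiday: 7 − 8 = −1 for Monday to Thursday and Sunday, 7 − 9 = −2 for Saturday, and 7 − 10 = −3 for Friday. Causality then falls due 1 to 3 days after the FDA report.
- Next-day notice, weekday, no holiday: 1 + 7 − 7 = 1 day.
- Notice at the 3-working-day limit, no holiday: from 3 + 7 − 7 = 3 (Monday, Tuesday) to 5 + 7 − 7 = 5 (Wednesday to Friday). With a holiday the range is 2 to 5.

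**Step 4. The two results are alternatives.** The 12-day path needs a site that uses all 3 working days, and causality is then due 3 to 5 days before the FDA report. The zero or negative margin needs a site that reports at or near once. One event cannot show both.

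Step 3 also shows that shortening first notice alone would take the weekday margin from 3 to 5 days down to 0 or 1. A shorter limit therefore has to come with a relationship rating in the same entry.

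**The case against.** The 3 working days are an outer limit on a duty to report as soon as possible. Section 2 covers only deviations that may affect safety and welfare, gives no number of hours, and refers to each institution's guidelines. Sections 5.4.1 and 5.4.2 do not contradict each other. The figure of 24 hours is not in the documents. The study is non-interventional (section 3.2). Subjects must have had all injections through Day 104 (section 3.3.1), and consent starts at Day 270 (section 3.4.3), which is 270 − 104 = 166 days later. Faster notice cannot change any extension subject's dosing. The DSMB meets periodically, so a few days would seldom alter its work.

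All of that stands, and it limits the point to a modest one. It does not remove the outer limit, which a compliant site may use in full for a death.

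Four stronger readings are tempting, and the documents do not support them.
- *A missing causality opinion stops the 7-day report.* Section 5.4.2 does not make that report depend on relatedness. Causality matters for classifying suspected adverse reactions, and so for the 15-day report, whose clock starts at the sponsor's own determination.
- *The initial report lacks expectedness and causality.* Expectedness is selected at that entry. Relationship is an AE worksheet field (section 5.2), and the worksheets match the EDC pages (section 12), so it may well arrive then. Section 5.4.1 still allows 5 working days for it.
- *A signed form is the only possible route.* Section 5.4.1 explains the signature as a filing need and does not say that an unsigned report is refused. Contact pages are absent from the public copy, so another route may be given there.
- *A holiday adds just one day.* It adds one day to the 5-working-day limit from Monday to Thursday, but three from Friday to Sunday.

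**Conclusion.** The point holds as a low-cost improvement to safety reporting. With every limit met, an unexpected fatal or life-threatening event can take up to 12 calendar days from the investigator's awareness to FDA, or 13 with a holiday, against 8 with notice within a day. First notice of a death may take 3 to 5 calendar days (6 with a holiday), while a safety-relevant deviation is to be reported immediately.

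The causality overlap is a separate and smaller matter. When a site reports at once on a weekday, the opinion may fall due on the day of the 7-day report, or 1 to 3 days after it if a holiday intervenes. The sponsor may then have to file without it.

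The figures rest on a Monday-to-Friday week, awareness as day 0, and at most one holiday. They start from the investigator's awareness. Section 4.3 has the study coordinator telephoning subjects, so site staff may hear of an event sooner, and the true interval could then be longer. The benefit is to oversight and to any other VM202 recipients, whom the documents do not identify.

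**What to change.** In Protocol section 5.4.1:

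1. Bring first notice of SAEs, at least fatal and life-threatening ones, into line with the standard of section 2. A limit of 24 hours from the time site staff learn of the event is one example. That number is a suggestion and does not come from the documents.
2. State that the relationship field is completed provisionally in that entry, so that the sponsor has an opinion before the 7-day report is due.
3. Let the signature, narrative and source documents follow within the existing 5 working days, so that an absent signatory does not delay the alert.

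Expectedness needs no new text, because the initial entry already captures it. The cost is protocol wording and a note to sites. The drawback is that some initial reports will be incomplete and need a follow-up entry. No analysis in the SAP changes.

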5.4.2. SPONSOR'S RESPONSIBILITY

All AEs and SAEs will be reported on an annual basis to FDA in accordance with the IND regulation (21 CFR Part 312). Per the 2010 FDA Guidance Document for Industry and Investigators "Safety Reporting Requirements for INDs and BA/BE Studies," events categorized as 'possibly' or 'probably' related will be treated as 'suspected adverse reactions.' Events categorized as 'definitely' related will be treated as an 'adverse reaction.'

All serious, unexpected adverse reactions and suspected adverse reactions will be reported to FDA and to all participating investigators as an IND Safety Report within 15 calendar days of the event after the sponsor determines that the suspected adverse reaction qualifies for reporting (21 CFR §312.32). Any unexpected fatal or life-threatening AEs will be reported to the Agency within 7 calendar days after the sponsor's initial receipt of the information.

The Sponsor will notify all participating investigators of any new safety information that alters the current risk-benefit assessment of the study medication or that would be sufficient to consider changes in VM202 administration or in the overall conduct of the trial.

5.5. ANALYSIS POPULATION

The analysis population will be the safety population, and will include all subjects who sign consent for the safety extension study. Subjects in the analysis population

will be analyzed according to treatment received, regardless of original treatment assignment. The primary analyses of the primary and secondary endpoints will be based on the analysis population.

5.6. STUDY ENDPOINTS

5.6.1. PRIMARY ENDPOINTS

The primary endpoint is the difference in long-term safety – defined as occurrence of adverse events - observed between subjects receiving VM202 versus subjects receiving placebo in the VMDN-003 study.

5.6.2. SECONDARY ENDPOINTS

The secondary efficacy endpoints are:

- 1. The change in the average 24-hour pain score from baseline to the Day 365 follow-up from the Daily Pain and Sleep Interference Diary;
- 2. The change in the average 24-hour pain score from Day 270 to the Day 365 follow-up from the Daily Pain and Sleep Interference Diary; and
- 3. Patient's Global Impression of Change (PGIC) at the Day 365 follow-up.

5.6.3. ANALYSIS METHODS

The statistical analyses will be descriptive only and reported using summary tables, figures, and listings. All summaries will be derived based on available data. The average 24-hour pain score for a visit will be considered as missing if fewer than 5 of 7 days of Daily Pain and Sleep Interference Diary entries are provided. No imputation will be performed for missing values. Summary tables will present results by treatment group (i.e., VM202 and Placebo) both within and across the randomization stratification factor (i.e., baseline use of gabapentin and/or pregabalin) values. Continuous variables will be summarized using the number of non-missing values, mean, standard deviation, median, minimum and maximum values. Categorical data will be summarized using the number of observations and percentages. Summary plots of efficacy data will present mean values with standard error bars.

5.6.4. DATA SAFETY MONITORING BOARD (DSMB)

The independent data safety monitoring board (DSMB) for the VMDN-003 study will periodically review a limited set of un-blinded tables and/or listings, including all reported AEs, as per its responsibilities described in the DSMB Charter. The objectives of the DSMB meetings are to review the safety outcomes of the study and provide guidance to study sponsor regarding the safety of the VM202. The data analyses for the DSMB meetings will be provided to the DSMB members and other participants of the DSMB meeting.

6. ACCESS TO STUDY DOCUMENTS AND STUDY MONITORING

The Sponsor has designated consultants to monitor the progress of this study. The clinical monitor, as a representative of the Sponsor, has the obligation to follow this study closely.

The Sponsor or its designee may meet with investigators prior to the initiation of the study in order to review the adequacy of the subject population, facilities, and equipment with respect to the needs of the study, and to familiarize the investigator with the study protocol.

The Sponsor or its designee may meet with the investigator(s) at the time study subjects begin to be enrolled in order to ensure that subjects are being properly selected and that study data are being correctly recorded.

During the study, the clinical monitor will visit the study facilities regularly, and utilize telephone and written communications on an ongoing basis to maintain current knowledge of the study. During periodic visits to the study site, the monitor will review the study worksheets used for data entry in the EDC system to verify the accuracy and completeness of the information contained in those reports in preparation for retrieval. Study worksheets and source documents must contain all data entered in the EDC system. All data generated during this study and the study worksheets/source documents from which they originated are subject to inspection by the Sponsor or its representatives, the FDA and other regulatory agencies.

Upon completion of the study, the clinical monitor will conduct a final visit (close-out) to the site. The objectives of this visit are to ascertain that all regulatory records and reports are complete, verify that study drug and other supplies have been accounted for and ensure that the investigator is aware of his/her responsibilities post-study.

7. QUALITY CONTROL AND ASSURANCE

The Sponsor employees and/or their contracted representatives utilize Standard Operating Procedures (SOPs) designed to ensure that research procedures and documentation are consistently conducted/prepared to the highest quality standards. These SOPs also require compliance with Health Authority regulations and Good Clinical Practice guidance.

A Quality Assurance audit may be conducted by the Sponsor or its designee at any time during or after completion of a study. The Investigator will be given adequate notice if he/she is selected for an audit. The audit will include, but is not limited to, a review of all informed consent forms, a review of study worksheets, associated source documents and medical records, a review of regulatory documentation, an assessment of study conduct and protocol compliance, and a review of the investigational drug accountability. At the conclusion of an audit, the auditor will conduct a brief meeting with the Investigator to review the findings of the audit.

8. INSTITUTIONAL REVIEW BOARD

Prior to the initiation of the study, the protocol, the informed consent form and investigator's brochure will be submitted to the IRB for approval. By signing the "Statement of Investigator" form (form FDA 1572), the investigator is assuring that an IRB which complies with the requirements set forth in 21 CFR Part 56 will be responsible for the initial and continuing review of the proposed clinical study. A copy of the IRB approval letter for the protocol, the informed consent, and the protocol signature page must be submitted to the Sponsor or its designee, prior to release of investigational supplies to the study site. The approval letter must refer to the specific protocol and the informed consent form. The study site must maintain an accurate and complete record of all reports, documents and other submissions made to the IRB concerning this protocol. A list of the IRB members, their titles or occupations, and their institutional affiliation, or an IRB assurance number must be provided to the Sponsor or its designee prior to release of study supplies.

FDA/relevant health authority regulations require that all advertisements for subject recruitment be approved by an IRB prior to implementation. The complete text and format must be submitted to the Sponsor or its designee for approval prior to IRB submission.

The investigator is responsible for notifying the IRB of any serious adverse events as required by the IRB.

Status reports must be submitted to the IRB at least once a year (or more frequently as required by the IRB) and the IRB must be notified of completion or termination of the study. A final report must be provided to the IRB and the Sponsor within 1 month of study completion or termination. This report should include: any deviations from the protocol, the number of participants evaluated, the number of participants who withdrew or were withdrawn and the reasons for withdrawal, any significant adverse events and the investigator's summation of the study.

9. **INFORMED CONSENT PROCESS**

It is the responsibility of the investigator or designee to inform each subject, prior to the screening evaluation, of the purpose of this clinical trial, including possible risks and benefits and document the informed consent process in the subject's chart. A sample informed consent form containing the required elements of informed consent is provided in Appendix 1. Any changes made to this sample must be approved by the Sponsor or its designee, prior to submission to an IRB. After approval by the Sponsor or its designee, the informed consent must be submitted to and approved by an IRB. Prior to entry into the study or initiation of any study-related procedures, the subject must read, sign and date the informed consent form. The person executing the consent must also sign and date the final consent form page. One original informed consent form is to be retained by the study site and a copy is to be given to the subject. The informed consent process must be documented in the subject's medical record.

The informed consent must be written in a language in which the subject is fluent. If a foreign language translation is required, a statement of certification of the translation must be issued. Regulations require that foreign language informed consent forms be submitted to the IRB for approval. The investigator must forward a copy of the consent form, the certified foreign language translation and an IRB approval letter to the Sponsor or its designee.

